**2. Quality Comparators (Outcomes for Aim 2 and exposures for Aims 3 and 4)**

Each quality comparator is made up of patient or proxy answers to several questions rated either as: "very satisfied, satisfied, dissatisfied, or very dissatisfied" or as: "strongly agree, agree, disagree, or strongly disagree" during the patient's baseline interview. Higher values will be coded to represent negative connotations. The comparators and component questions address: **Comparator 1: Care Coordination and Quality:** 5 questions on overall quality of care, information given, follow-up care, concern for overall health, and needs met at same location. **Comparator 2: Access Barriers:** 3 questions on availability of night/weekend, ease/convenience, and out-of-pocket costs. **Comparator 3: Technical Skills of PCP:** 3 questions about checking "everything", understanding medical history, and understanding what is wrong. **Comparator 4: Interpersonal Skills of PCP:** 4 questions about whether or not the PCP is in a hurry, does not explain, does not discuss, and acts like doing a favor. **Comparator 5: Quality of Information provided by PCP:** 4 questions about whether the PCP "tells all I

PRINCIPAL INVESTIGATOR (LAST, FIRST, MIDDLE): [name]

want to know,” “answers all my questions,” “has my confidence,” and dependence on doctor(s) to “feel better both physically and emotionally.” Combination of these questions into 5 comparator measures is supported by factor analyses with factor loadings of items on the 5 scores of 0.55 or greater. Cronbach’s coefficient alpha was 0.82 for global quality, 0.54 for access barriers, 0.89 for PCP technical skills, 0.79 for interpersonal manner, and 0.84 for Information giving. Average item-level responses will be determined for each variable. Comparators 1 and 2 will be available for all patients, but PCP comparators only for the approximately 90% of patients who have regular PCPs. Comparators will be presented trichotomously, addressing high and low quality extremes. For the access and quality comparators, the best and worse access and quality will be compared to the middle quartiles. For the PCP comparators, no PCP and quality in the highest quartile will be compared to the 3 lower quartiles similar to the approach taken by Lee and Casper.

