**Aim 2** will address the degree to which people with disabilities experience healthcare disparities. The comparators will be the outcome here and ADL/IADL stages will be the main exposure. We will model each trichotomously expressed comparator through multinomial logistic regression. We will report adjusted relative risk ratios (RRRs) and their 95% confidence intervals (CIs) for the ADL and IADL stages (stage I as reference). For each continuously expressed comparator, we will report sample weighted estimates for the ADL and IADL stages (stage I as reference) obtained through linear regression.

**Aim 3** will determine if people who experience better access and higher quality healthcare and who rate their PCPs highly on technical skills, inter-personal manner, and the provision of sufficient information to understand their health condition(s) will be less likely to experience a negative transition outcome. The 5-state transition outcome will be modeled by multinomial logistic regression models with no change in function as reference. We will report RRRs and their 95% CIs. In the multinomial logistic regression, the relative risk of improvement in function, decline in function, institutionalization, or death will be defined as the probability of improvement in function, decline in function, institutionalization, or death divided by the probability of remaining at the same ADL stage.

Each of the 5 comparators will be modeled individually after considering other covariates. They will also be entered into one model to determine the relative independent effects of each after considering the other exposures.

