**Aim 4** While models for aims 2 and 3 will be etiological and explanatory, the policy simulations will be predictive. We will simulate the maximum benefit of healthcare programs or policies aimed at improving each comparator, i.e., coordination and quality of care, increasing access, PCP technical skills, PCP interpersonal skills, and the quality of information provided by PCPs on likelihood of functional improvement, functional decline, institutionalization, or death over 1, 2, and 3 years. Taking the scenario of increased access as example, the simulation will: estimate the effect of poor access to care according to the transition outcome using  $\beta$ -coefficients from a multinomial regression similar to those proposed in Aims 2 and 3, i.e., we will use coefficients to predict status according to the multiple outcome states of "improved in function," "deteriorated in function," "institutionalized," and "died" by 1-, 2- and 3-year follow-up compared to "remained at the same ADL stage," given the new optimized access comparator, while holding baseline ADL stage and all other variables constant at the individual-levels. This will allow creation of new population prevalence estimates for each of the outcome states assuming optimal access. Comparison of these predicted/adjusted values and their associated confidence intervals will show the relative potential of policies targeted to improve the access comparator (when compared to any other policy change scenario) included in the simulation. Simulations will be performed for the 1-, 2- and 3-year time frames and for ADL and IADL stage transitions. This will produce a table showing the regression-based, predicted effects of optimizing alternative comparators on population status. These simulations will help frame the results of our study according to the "comparative effectiveness" of alternative policy instruments targeted to the 5 quality comparators. These findings will be triangulated with thematic materials extracted from the stakeholder groups (see above).

PRINCIPAL INVESTIGATOR (LAST, FIRST, MIDDLE): [name]

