Quantitative: ADL and IADL are fundamental. Yet, other activities such as driving and additional unobservable cofounders could bias interpretations. We minimized unobservable confounders by selecting a content-rich data source. Recall bias which in surveys can be problematic is minimized in the MCBS by having people keep records. Around 18% of Medicare beneficiaries refuse to participate in the MCBS which could potentially reduce generalizability. Studies of the MCBS data indicate that bias caused by differences between non-responders and responders was small and substantially reduced by the non-response procedures employed. MCBS cumulative response rates by the fourth year range between 63-68%. Recognizing that lost to follow-up may be more common among those with substantial disabilities, we will include post-stratification weights to minimize potential effects of differential non-response, and adjust the weight further by considering propensity to drop out.

PRINCIPAL INVESTIGATOR (LAST, FIRST, MIDDLE): [name]

We will also impute missing data using SAS callable IVEware software 0.2 through multiple imputation. After generating 5 multiple imputation datasets, we will conduct all analyses allowing inclusion of all subjects. We will compare findings across the different analytical approaches. Also, we acknowledge that this observational design is not causal; however, the mixed methods design and use of large broadly representative populations enhance validity. Finally, it is essential to recognize the essential patient centeredness of this project. We will be addressing patients' perceptions of and beliefs about healthcare quality and physician competence. Conclusions that might be drawn from patient perceptions and professional measures may differ.

**Study population:** See description in study sample section.

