**Quantitative: Overview and General Approach to Multivariable Estimation:** Our specific aims focus on empirically quantifying disparities in the quality of health and PCP care as perceived by PWD compared to PWOD and the impact of any disparities identified on transition outcomes. Taking advantage of the large nationally representative contemporary cohort of Medicare beneficiaries enrolled over a decade in the MCBS, quantitative methods will begin by

PRINCIPAL INVESTIGATOR (LAST, FIRST, MIDDLE): [name]

exploring the associations of all covariates to ADL and IADL stage transitions over 1, 2- and 3-year periods. A series of multivariable regressions will be implemented in Aims 2, 3, and 4 to provide a comprehensive perspective on disparities and the factors influencing transitions. After quantifying the net contribution (if any) of each comparator to outcome transitions, we will then use parameter estimates generated by these analyses in the Aim 4 simulation study. The goal will be to simulate the maximum effect of alternative programs intended to improve access to care, quality of care, and the technical and other qualities of PCPs on the wellbeing of the US Medicare population.

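### Comparators 3-5 share one no-PCP group, so their no-PCP effects cannot be separated in the joint model, and Aim 4 does not say how its PCP scenarios treat that 10%

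*Combined protocol and SAP*

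**What the plan says.** - **Coding.** Under 2. Quality Comparators, comparators 1 and 2 exist for everyone, "but PCP comparators only for the approximately 90% of patients who have regular PCPs". Comparators 3 (technical skills), 4 (interpersonal skills) and 5 (information) each have three levels: "no PCP and quality in the highest quartile will be compared to the 3 lower quartiles".
- **Aim 3 (Data Analysis).** Each comparator is first modelled alone with covariates. "They will also be entered into one model to determine the relative independent effects of each after considering the other exposures".
- **Aim 4 (Data Analysis).** One comparator at a time is set to its optimum, "while holding baseline ADL stage and all other variables constant at the individual-levels", and new population prevalences are predicted. The worked example is access, which has no no-PCP level. The coefficients come from "a multinomial regression similar to those proposed in Aims 2 and 3". The aim is comparative: "Comparison of these predicted/adjusted values and their associated confidence intervals will show the relative potential of policies".
- **Project Plan and Timeline, quantitative overview.** On where the simulation's inputs come from: "After quantifying the net contribution (if any) of each comparator to outcome transitions, we will then use parameter estimates generated by these analyses".

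The plan has no shared no-PCP indicator and no rule for people without a PCP in the joint model or the simulation.

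**The concern.** A person without a PCP lacks one for all three PCP comparators, so the three no-PCP indicators are one column entered three times. The joint model can estimate their total effect but cannot divide it among technical skills, interpersonal skills and information.

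This matters once coefficients are used one comparator at a time. Setting one PCP comparator to best while holding the rest fixed moves a person without a PCP into a combination that cannot occur. The predicted benefit then includes whatever share of the no-PCP effect the software happened to assign to that comparator. Aim 4 is meant to compare policies, so what is at stake is the size of the three PCP policy benefits, under some inputs their order, and their comparison with comparators 1 and 2.

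**Working it through.** **Inputs from the plan.** About 90% have a regular PCP, so about 10% do not. Table 5 gives 12,058 people in 3 panels and expects 40,000 in 10. Check: 12,058 x 10/3 = 40,193, consistent with 40,000. The no-PCP group is then about 0.10 x 40,000 = 4,000.

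**Inputs assumed, because the documents give none.** Reference risks: improvement 8%, deterioration 15%, institutionalization 2%, death 5%, hence no change 70%. Best-quartile RRRs for comparators 3/4/5 are 0.90/0.85/0.95 on the three adverse outcomes. The correlation between PCP scores is 0.6. The no-PCP RRR, R, on the adverse outcomes is varied from 0.8 to 2.0.

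**Step 1: estimability.** Columns per outcome equation: intercept 1 + comparators 1-2 (4) + no-PCP (3) + best quartile (3) = 11. Three columns are identical, so the rank is 11 - 2 = 9. A simulated design with 40,000 people confirms this; adding four ADL stage indicators gives 15 columns, rank 13. Only the three no-PCP coefficients fail the estimability check; their sum passes. Each single-comparator model has full rank. The rank result does not depend on the assumed risks.

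**Step 2: Aim 4 with joint-model coefficients.** Let S = log R be the sum of the three no-PCP coefficients and b_j the best-quartile coefficient. For a person without a PCP, optimizing comparator j moves the linear predictor from S to b_j if column j is the one kept, and from S to S + b_j if it was dropped. With x the linear predictor, the deterioration risk in percent is 100 x 15e^x / (78 + 22e^x), where 78 = 70 + 8 and 22 = 15 + 2 + 5.

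At R = 1.5 the starting risk is 22.5/111 = 20.27%. For technical skills:

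- column kept: 13.5/97.8 = 13.80%, a fall of 6.47 points, times 10% = 0.65;
- column dropped: 20.25/107.7 = 18.80%, a fall of 1.47 points, times 10% = 0.15.

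People with a PCP contribute 0.79 either way, so the population benefit is 1.44 or 0.94. For all three scenarios, as percentage-point fall in deterioration:

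| Column kept | Technical | Interpersonal | Information |
|---|---|---|---|
| Technical | 1.44 | 1.43 | 0.46 |
| Interpersonal | 0.94 | 1.92 | 0.46 |
| Information | 0.94 | 1.43 | 0.98 |
| People with a PCP only | 0.79 | 1.21 | 0.39 |

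The shift is about 10% x (20.27% - 15.00%) = 0.53 points. First place in the top row is a near tie, not a reversal.

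**Step 3: range.** There were 36 assumed settings: deterioration risk 10/15/20%, correlation 0.3/0.6/0.8, and four sets of best-quartile effects.

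| R | Shift per scenario (points) | Settings where the top PCP policy depends on the kept column |
|---|---|---|
| 0.8 | 0.15-0.31 | 9 of 36 |
| 1.0 | 0 | 0 of 36 |
| 1.2 | 0.14-0.28 | 9 of 36 |
| 1.5 | 0.33-0.64 | 15 of 36 |
| 2.0 | 0.62-1.15 | 30 of 36 |

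A separate simulation with other assumed inputs (true R = 1.3) moved technical skills from 0.05 to 0.36 points while information stayed at 0.33, so those two changed order. Predictions for people with a PCP did not move.

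**Step 4: Aim 4 with single-comparator coefficients.** Here the no-PCP group's contribution is estimable. In the base case it adds, for technical/interpersonal/information:

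- R = 0.8: about zero
- R = 1.0: 0.24/0.27/0.21
- R = 1.2: 0.46/0.49/0.44
- R = 1.5: 0.77/0.79/0.74
- R = 2.0: 1.20/1.23/1.17

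The three additions are nearly equal at each R, and the order of the PCP policies stays the same throughout. In the separate simulation the three no-PCP log RRRs for deterioration were 0.284, 0.267 and 0.280: in effect one contrast counted three times.

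**The case against.** The strongest reply is that the plan never commits to the steps that cause harm. Aim 4 does not name the joint model; the single-comparator models come first in Aim 3 and have full rank. A net contribution of each comparator may mean net of covariates rather than of the other comparators. The worked example concerns access, so no PCP scenario is spelled out. Software will drop two columns and return correct best-quartile contrasts. Aim 4 asks for a maximum benefit, which might be taken to include gaining a PCP. Variable definitions and analysis plans are due in Month 9, and final variable specifications in Year 1.

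Much of this stands, and it limits the point. A reader might infer that Aim 3's PCP results are invalid; they are not, since only the split of the no-PCP effect is lost. A reader might infer that the ranking of PCP policies is arbitrary; that needs joint-model coefficients and a non-null no-PCP effect, and even then occurs only under some inputs. Nor does the statement that "we will conduct all analyses allowing inclusion of all subjects" settle the matter: it describes the multiply imputed datasets, and having no PCP is a defined category, not a missing value.

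What does not stand is that this is merely an omitted detail. The coding is stated, and so is the rule of changing one comparator with all others fixed for each individual. Applied together to everyone, they produce the impossible combination, and neither candidate coefficient source removes it. Automatic dropping of columns makes the problem easy to overlook. If gaining a PCP is part of the target, it is one policy and should not be credited to three quality dimensions.

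**Conclusion.** The point holds in a limited form. It is certain that the joint model identifies only the sum of the three no-PCP coefficients. Best-quartile contrasts, comparators 1-2 and predictions for the roughly 90% with a PCP are sound.

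The consequence for Aim 4 is conditional on PCP scenarios being applied to everyone as the general rule reads. With joint-model coefficients, the no-PCP group's benefit depends on the kept column: about 0.5 points in the base illustration at R = 1.5, and no dependence at all if the adjusted no-PCP effect is null. With single-comparator coefficients, the benefit is determined and the order of the PCP policies is largely kept, but each carries a nearly equal credit for gaining a PCP. That distorts their size and their comparison with comparators 1-2, and in the base case it is present even at R = 1.0. Every magnitude is illustrative. The matter should be settled before the simulations are run.

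**What to change.** 1. Code one shared indicator for having no regular PCP, and define comparators 3-5 among people with a PCP. The joint design then has full rank: 9 of 9 columns, or 13 of 13 with ADL stage.
2. Name the model, joint or single-comparator, that supplies the Aim 4 coefficients.
3. Apply PCP-quality scenarios only to people with a PCP, leave the others at their observed state, and say so beside the results.
4. If the effect of gaining a PCP is of interest, simulate it as a separate scenario.

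The cost is a small recode of existing variables and a few sentences; no new data are needed and no estimable coefficient is lost. The downside is that PCP-quality benefits then refer to the roughly 90% with a PCP, whereas comparators 1-2 apply to everyone, so the comparison table should state whom each scenario changes.

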Activity Limitation Stages determined during the baseline fall interview will be the key independent variable (see Table 1 for definitions). ADL stages (0-IV) will be primary and IADL stages (0-IV) analyzed secondarily. IADLs such as meal preparation are not always relevant when someone else is available to perform those tasks, yet IADL enables exploration of the effects of milder disabilities.

Other covariates: *Working age* 21 to 64 and 65 and over; *gender*; *race* (African American or Black, Hispanic, White, and other); *education* (high school graduation Y/N); *marital status* (married/unmarried); *income* (Medicare categories of annual household income from all sources); *insurance type* (Medicare only, Medicare and Medicaid-dual enrollee, private-supplemental, other (i.e., Champus, VA)); *living arrangement* (i.e., lives alone or with spouse only, with children, with other relatives or non-relatives, or in a retirement community); and the *presence or absence of accessibility features in the home* (home accessibility features). Health status will be captured by physician-reported *chronic conditions and impairments* (hypertension, asthma, diabetes, COPD, coronary artery disease, and congestive heart failure, intellectual and/or developmental disability, dementia or Alzheimer’s disease, neurological disorders, mental illness, no usable vision, and deaf). Building on our previous work, we know that the nature and severity of disabilities resulting from these conditions can be expected to vary. As example, neuropsychiatric conditions, particularly those causing intellectual disabilities, are often extremely disabling, while people who are blind or deaf often find ways to accommodate and perform basic activities. Analyses will control for residence based on Census regions.

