#### Data Analysis

Complex survey design: The MCBS uses a multi-stage clustering sample with unequal sampling probabilities. We will take into account the complex design by using appropriate survey commands in Stata to calculate the correct point estimates and their variances. Specifically, the set of longitudinal weights (RIC X2) allowing analysis of data trends over a two year period and a second set of longitudinal weights (RIC X3) will be applied to two- and three-year outcomes.

Proxies: Proxy responses will be included in all models. About 9.8% of MCBS baseline interviews were conducted by proxies and our previous work indicates that exclusion of proxy responses results in underestimates of disability prevalence. Recognizing this may explain proxy differences we will explore replacing proxy status with reason for proxy use.

Missing data and attrition: See Avoidance of Bias below.

General approach to analysis: Each Aim will describe the sample of Medicare beneficiaries with weighted uni-variable summary statistics appropriate to the distributional characteristics of the variables of interest and bi-variable associations with outcomes. Because of concerns that some variables may be intermediate on causal pathways, to understand associations, we will build etiological models hierarchically. All will control for baseline age, gender, race, ADL or

PRINCIPAL INVESTIGATOR (LAST, FIRST, MIDDLE): [name]

IADL stage, and proxy status. Health conditions and living circumstances will be added sequentially, selected according to associations with functional change, institutionalization, or mortality or according to emergent themes from stakeholder groups. The Goodness-of-Fit (GOF), Deviance and Pearson GOF Statistic, ROC curve, and r-square values as appropriate to each regression will be reported to document model fit of the multinomial regressions. Stata 11.0 (Stata Corp, College Station, Texas) will be used for all analyses (except for multiple imputation as noted below). A 2-sided  $p<.05$  will be used for all final tests of significance.

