#### **QUANTITATIVE: PROTECTION OF HUMAN SUBJECTS: RISKS TO THE SUBJECTS:**

**Human Subjects Involvement and Characteristics** This research involves the study of existing “limited” data and diagnostic records in a series of databases available from the Centers for Medicare and Medicaid Services (CMS). Data will be merged from the Medicare Current Beneficiary Survey (MCBS) Access to Care files which will be obtained from the Research Data Assistance Center (ResDAC). ResDAC is a CMS contractor (Contract Number

PRINCIPAL INVESTIGATOR (LAST, FIRST, MIDDLE): [name]

HHSM-500-2005-00027I) that provides free assistance to academic, government, and non-profit researchers interested in using Medicare and/or Medicaid data for research.

Based on analysis of the 2006 MCBS data, there are no children involved in this study. The subjects range in age from 22 to over 85 years of age. Disabled persons under the age of 65 and very old persons of the age of 80 and over are oversampled. Age-wise, 82.63% of the Medicare beneficiaries are at least 65 years of age and older and 17.37% are people younger than 65 years of age who either have disabilities or severe chronic illnesses. Among the 82.63% of Medicare beneficiaries who are 65 years and older sub-group, 40.52% are between 65 and 74 years old, 40.55% are between 75 and 84 years old, and 18.93% are 85 years and older. Among the 17.37% disabled Medicare beneficiaries sub-group, 50.57% are 22 to 44 years old and 49.43% are 45-64 years old. Gender-wise, 44.30% of Medicare beneficiaries are male and 55.70% are female. In terms of ethnicity, 84.43% of Medicare beneficiaries are White non-Hispanic, 10.30% are Black non-Hispanic, 2.33% are Hispanic or Latino, and 2.94% are classified as other.

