**The following types of Protected Health Information (PHI) will be used in the study, with reasons for use highlighted:**

Birth dates, sex, ethnic code, functional status, diagnoses, dates of hospitalizations, and dates of death will be used in the project analyses. The project requires functional status information to define the Activity Limitation Stages. The project requires diagnoses to define disabling impairments as covariates. Admission dates to functional status, nursing home, and death dates are required for the outcomes. These data are fundamental to the aims. Ages will be grouped in categories. Eighty-five years of age and above is the oldest category. Data will be presented only in aggregated form. Socioeconomic information will be necessary to adjust outcomes for the effects of these differences.

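### The plan states the coding of age inconsistently, and the only itemised definition (under 65 versus 65 and over) would be too coarse for models of death and institutionalization

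*Combined protocol and SAP*

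**What the plan says.** Four places bear on age.

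- The Other covariates paragraph, which follows the description of the quality comparators in Part C, lists one age item. It is labelled as working age and has two levels: "21 to 64 and 65 and over". No other list in the plan itemises the covariates.
- Data Analysis, general approach: "All will control for baseline age, gender, race", together with ADL or IADL stage and proxy status. No functional form for age is given. Health conditions and living circumstances are added afterwards, in sequence.
- The section on the types of Protected Health Information to be used includes birth dates among the elements for the analyses, and adds: "Ages will be grouped in categories. Eighty-five years of age and above is the oldest category".
- The quantitative Human Subjects section describes the population from 2006 MCBS data: "82.63% of the Medicare beneficiaries are at least 65 years of age and older" and "17.37% are people younger than 65 years of age". It then divides the older group into 65-74, 75-84 and 85+.

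The paragraph on the Patient-Informed Surveillance Tool uses the working-age versus elderly distinction for another purpose: possible effect modification, leading to separate Tools.

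**The concern.** A split at 65 and a set of categories topped at 85+ are different variables, and the rule that puts age into every explanatory model does not say which one it means. A programmer working from the covariate list would enter a single indicator. A person of 66 and a person of 92 would then receive the same age adjustment in a model whose outcome states include death and institutionalization.

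Two things would follow.

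- **Aim 3 and Aim 4.** If a comparator also varies with age within 65+, part of the age effect on death or institutionalization is attributed to the comparator. Aim 4 uses the fitted coefficients to predict outcomes under improved care, so the error carries forward. It could also distort the comparison between policies if the five comparators have different age patterns.
- **The Tool.** Points come from regression coefficients. With two-level age, everyone over 65 receives the same age points. This loss requires only that risk changes with age beyond 65; satisfaction need not vary with age.

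**Working it through.** **Consistency of the plan's figures.** The age percentages come without counts, so only their sums can be checked: 82.63 + 17.37 = 100.00 and 40.52 + 40.55 + 18.93 = 100.00. As shares of all beneficiaries, the three older bands are 0.8263 × 40.52 = 33.5%, 0.8263 × 40.55 = 33.5% and 0.8263 × 18.93 = 15.6%. The largest single age stratum is therefore 82.6% under the two-level coding and 33.5% under the bands that the plan itself reports.

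**Size of the possible bias.** Collapse the three 65+ bands into one, with no effect of dissatisfaction on death inside any band, and compute the odds ratio that appears.

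Inputs:
- weights w = 0.4052, 0.4055, 0.1893 (Human Subjects section);
- 3-year mortality m, assumed: steep 6/15/36% or shallow 8/14/25%;
- share dissatisfied s, assumed, as in the table.

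The documents give neither gradient.

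Formula: a = Σwsm, b = Σws(1−m), c = Σw(1−s)m, d = Σw(1−s)(1−m), OR = ad/(bc).

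Worked case, steep mortality with s = 16/13/10%:
- a = 0.4052×0.16×0.06 + 0.4055×0.13×0.15 + 0.1893×0.10×0.36 = 0.01861
- Σws = 0.13648, so b = 0.13648 − 0.01861 = 0.11787
- Σwm = 0.15328, so c = 0.15328 − 0.01861 = 0.13467
- d = 1 − 0.13648 − 0.13467 = 0.72885
- OR = (0.01861 × 0.72885)/(0.11787 × 0.13467) = 0.85

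| Dissatisfied at 65-74/75-84/85+ | OR, steep mortality | OR, shallow mortality |
|---|---|---|
| 18/13/8% | 0.77 | 0.85 |
| 16/13/10% | 0.85 | 0.91 |
| 14/13/12% | 0.95 | 0.97 |
| 13/13/13% | 1.00 | 1.00 |
| 11/13/18% | 1.19 | 1.12 |

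**Second set of assumptions.** Take 3% mortality and 15% exposed at 65-74, with the odds of death multiplied by 1.5 to 3 per band and the odds of exposure by 0.8 to 1.5 per band. The same calculation gives 0.875 to 1.27. With the odds of death doubling per band and a weak exposure gradient (0.9 to 1.1 per band), it gives 0.96 to 1.04.

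**What these numbers are not.** They are unadjusted odds ratios of death against all survivors, for dissatisfied against everyone else. The plan's relative risk ratio sets death against remaining at the same stage, for dissatisfied against the middle category, after adjustment. The table shows the order of magnitude and does not predict the Aim 3 estimate.

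**The case against.** The strongest reply is that two-level age is not the settled specification. The item is labelled as working age, which reads naturally as a subgroup indicator, and the Tool paragraph uses it that way. The modelling rule says baseline age, birth dates are to be used, and the categories up to 85+ cannot be a split at 65. This stands: the documents leave the form unresolved, and a reader who concludes that binary age is fixed goes too far. The statement about categories does not settle the matter either, because it sits in a privacy section and may describe presentation.

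Three further inferences are tempting, and the documents do not support them.

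- **That the confounding is strong.** No age gradient in mortality or satisfaction within 65+ is given. The sign of the bias depends on the assumed direction, and a flat satisfaction profile gives none. Every explanatory model also includes stage and proxy status, and conditions are added later; these would take up some of the age effect.
- **That the bias rivals the effects in Table 4.** The 1.24 there is death for satisfied versus the middle group, and the 0.90 is functional improvement for satisfied versus the middle group. The matching cell, death for dissatisfied versus the middle group, is 1.71 (reciprocal 0.58), and every illustrated value lies inside that range. Table 4 also uses 1-year transitions, while the mortality assumed for the table above is over 3 years.
- **That 82.63% is the share of the study sample.** It is worded as a share of Medicare beneficiaries in 2006 data, without saying whether it is weighted. The survey oversamples the under-65s and those aged 80 and over, and the study excludes people in institutions at entry.

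What remains is that the one definition a programmer could apply is the coarse one, and that it conflicts with another section.

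**Conclusion.** The point holds as an inconsistency with a practical consequence. The covariate list, the modelling rule and the health-information section do not agree on age, and the two-level form alone would be too coarse for death and institutionalization. If it were used, the spurious unadjusted odds ratio within 65+ could be about 0.77 to 1.19 under the first set of assumed gradients. It would be 0.95-0.97 with a mild satisfaction gradient and exactly 1 with none. Adjustment for stage and conditions would reduce it by an amount that the documents do not allow one to calculate. Potentially material is the right description. The bias does not shrink as panels are added, and Aim 4 works from the coefficients themselves. The loss of prognostic detail in the Tool does not depend on any satisfaction gradient.

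**What to change.** In the Other covariates paragraph, state the form in which baseline age enters all Aim 2-4 models. Bands consistent with the rest of the plan would serve: 65-74, 75-84 and 85+, with the under-65s divided as in the Human Subjects section (up to 44, and 45-64). A spline in age would also do. Keep the under-65 versus 65+ split only as the effect modifier foreseen for the Tool. Refer to this definition in Data Analysis, and align the health-information section with it, saying whether its categories are for modelling or presentation.

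The cost is small. Five bands need four age terms instead of one. In the five-state model, with four non-reference outcomes, that is 3 × 4 = 12 extra coefficients. If the 2006 shares applied to the expected 40,000, the older bands would hold about 13,393, 13,403 and 6,257 people, which is ample. Birth dates are already among the elements to be used, so no new data are needed.
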